## 4.4 Subject Stopping Rules

Study drug dosing for an individual subject will be permanently discontinued for intolerable AEs that do not resolve to mild in severity (as defined in [Section 10.2.2.2](#)) or baseline within 48 hours of suspension of dosing and for study drug-related SAEs.

Administration of the study treatment will be discontinued if any of the following liver chemistry stopping criteria is met:

- Serum alanine aminotransferase (ALT) or aspartate aminotransferase (AST)  $\geq 3 \times$  ULN (upper limit of normal) and total bilirubin level  $\geq 2 \times$  ULN  
NOTE: Serum bilirubin fractionation should be performed if testing is available. If fractionation is unavailable, urinary bilirubin is to be measured via dipstick (a measurement of direct bilirubin, which would suggest liver injury).
- Serum ALT or AST  $\geq 5 \times$  ULN
- Serum ALT or AST  $\geq 3 \times$  ULN if associated with the appearance or worsening of rash or hepatitis symptoms (fatigue, nausea, vomiting, right upper quadrant pain or tenderness, fever, rash, or eosinophilia)

Any laboratory value that exceeds these limits should be repeated as soon as possible and, if confirmed, study treatment should be immediately discontinued. If a repeat laboratory assessment cannot be obtained within 3 days after receipt of the result showing the abnormal value, study drug should be discontinued.

A subject who meets the following ECG criteria will have study treatment discontinued:

- QTcF >500 msec or uncorrected QT >600 msec
- an increase in QTcF by  $\geq 60$  msec from Day 1 predose (baseline) with an absolute value of QTcF  $\geq 450$  msec (males) or  $\geq 470$  msec (females)

Treatment must be discontinued immediately in any subject who experiences a GTCS during the study if the subject had not had a GTCS prior to study entry. Subjects with worsening of seizures during the study should have treatment discontinued per investigator discretion. Unless consent for further follow-up is withdrawn, subjects who discontinue study drug for safety reasons should be followed in accordance with the schedule detailed in [Table 3](#).

Other reasons for treatment termination are provided in [Section 6.4](#).

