3.3.7. Definitions and Terminology

Age

The age of a subject is defined as the number of whole years between the subject's birth date and the date of informed consent.

Day 1 (Baseline)

Day 1 is the earliest day that study drug is initiated.

Study Day

Study Day is defined relative to Day 1 as follows: Study Day = Date of event – Date of Day 1 +1*(1 if date of event \geq Date of Day 1, 0 otherwise).

Study Visit

Study Visit is the nominal visit as recorded on the eCRF.

Baseline Value

For purposes of analysis, the baseline value is defined as the last non-missing value obtained prior to initiation of study drug.

Change from Baseline

Change from baseline for a given endpoint is defined as the Study Day X value minus the baseline value.

Percent Change from Baseline

Percent change from baseline for a given endpoint is defined as the Study Day X value minus the baseline value, quantity divided by the baseline value, multiplied by 100.

$$\text{Percent Change from Baseline} = (\text{Study Day X} - \text{Baseline})/\text{Baseline} * 100$$

Days on Study

Days on study is defined as the number of days from the date of study drug initiation to the final study visit (includes in home or in clinic assessments).

Completer

A subject is defined as a completer if he/she completes the Day 26 EEG and Day 27 dosing regardless of completing the Day 33 visit.

Treatment Period

The treatment period is the period during which a subject receives study drug (i.e., first dose through Day 27).

Days on Study Drug

Days on study drug is defined as the number of days in the treatment period. The date of the last dose of study drug as recorded on the End of Study Visit form or from the AICure electronic data transfer.

Total Study Drug Expected (capsules)

The total study drug expected is defined as the total number of capsules expected to be taken as recorded from all sources and reported from the AICure system.

Total Study Drug Received (capsules)

The total study drug received is defined as the total number capsules of taken as recorded from all sources and reported from the AICure system.

Total Study Drug Received (mg)

The total study drug received (mg) amount will be multiplied by 2 for subjects receiving CX-8998 to calculate the amount of study drug received in mg (i.e., each capsule is 2 mg).

Treatment Compliance

Treatment compliance will be calculated for each subject as a percentage using the following formula:

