5.3.2. Safety Analysis

5.3.2.1. Vital Signs and ECGs

Descriptive statistics will be presented for actual values and for the change from baseline values for systolic and diastolic blood pressure, pulse rate, respiration rate, and weight by study visit. Blood pressure summaries will include recumbent and standing measurements, as well as the change from recumbent to standing (orthostatic changes).

Incidence of vital signs outliers will be presented by visit and time point, where applicable. Outliers for recumbent and standing vital sign parameters will be determined using the criterion in Table 1.

Descriptive statistics will be presented for actual values and for the change from baseline values for the ECG parameters of heart rate (bpm), PR interval (msec), QRS duration (msec), QT interval (msec), QTc interval (msec), and QTcF interval (msec) will be summarized by treatment group and study visit.

The incidence of ECG outliers will also be summarized by visit according to the following criteria:

- $QT > 500$ msec
- $QTcF > 450$ msec for males or $QTcF > 470$ msec for females
- $QTcF$ increases from baseline or pre-dose:
 - ≤ 30 msec
 - > 30 msec to ≤ 60 msec
 - > 60 msec

Table 1. Outliers for recumbent and standing vital sign parameters

Vital Sign	Criteria
Temperature	>38°C and $\geq 1^{\circ}\text{C}$ increase from baseline
Pulse	>120 bpm and >30 bpm increase from baseline <50 bpm and >20 bpm decrease from baseline ≥ 20 bpm increase from baseline ≥ 40 bpm increase from baseline ≥ 20 bpm decrease from baseline ≥ 40 bpm decrease from baseline
Systolic blood pressure	>180 mmHg and with >40 mmHg increase from baseline <90 mmHg and with >30 mmHg decrease from baseline ≥ 20 mmHg increase from baseline ≥ 40 mmHg increase from baseline ≥ 20 mmHg decrease from baseline ≥ 40 mmHg decrease from baseline
Diastolic blood pressure	>105 mmHg and with >30 mmHg increase from baseline <50 mmHg and with >20 mmHg decrease from baseline ≥ 10 mmHg increase from baseline ≥ 20 mmHg increase from baseline ≥ 10 mmHg decrease from baseline ≥ 20 mmHg decrease from baseline

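### The SAP's ECG outlier table does not line up with the protocol's QT stopping limits, so on its own it cannot count the subjects who reached them

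*SAP*

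**What the plan says.** Protocol section 4.4 introduces its ECG limits with "A subject who meets the following ECG criteria will have study treatment discontinued". The first limit is "QTcF >500 msec or uncorrected QT >600 msec". The second is a QTcF rise of at least 60 msec "from Day 1 predose (baseline) with an absolute value of QTcF" of at least 450 msec in males or 470 msec in females. Both parts of the second limit must be met together.

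SAP section 5.3.2.1 plans a by-visit outlier summary (table 14.3.5.1.2 in SAP section 10): "The incidence of ECG outliers will also be summarized by visit according to the following criteria". It has three sets of rows:

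- uncorrected QT above 500 msec;
- QTcF above 450 msec (males) or above 470 msec (females);
- QTcF "increases from baseline or pre-dose", in the categories ≤30, >30 to ≤60 and >60 msec.

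SAP section 3.3.7 fixes baseline: "the baseline value is defined as the last non-missing value obtained prior to initiation of study drug". Note 8 to the schedule in SAP section 1.2 places predose and 1-2 hour postdose ECGs at both Day 1 and end of treatment (EOT). SAP section 7, which lists changes from the protocol's analyses, does not mention the ECG criteria.

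**The concern.** Change in QTcF is a named safety endpoint under the primary objective, and the protocol attaches a consequence to specific QT values. A reader of the study report will naturally turn to the ECG outlier table to ask how many subjects reached those values. If its thresholds differ from the protocol's, a zero in a row does not mean that nobody reached a limit, and a non-zero count does not mean that somebody did. If the change categories can be taken from an on-treatment tracing, they could also show less change than the drug produced.

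**Working it through.** **1. Limits side by side (msec)**

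| Protocol 4.4 limit | Nearest SAP 5.3.2.1 row | Difference |
|---|---|---|
| QTcF >500 | QT >500; QTcF >450 (M)/>470 (F) | The 500 row is on another quantity; the QTcF row has a lower threshold |
| Uncorrected QT >600 | QT >500 | Threshold 100 lower |
| QTcF rise ≥60 from Day 1 predose **and** QTcF ≥450 (M)/≥470 (F) | Rise >60; separately, QTcF >450/>470 | Counted separately, strict inequalities, reference not fixed |

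**2. The 500 msec row.** Fridericia's formula is QTcF = QT / (60/HR)^(1/3), so QT = QTcF × (60/HR)^(1/3).

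- QTcF 501 at 80 bpm: 501 × (0.75)^(1/3) = 501 × 0.9086 = 455.
- QTcF 501 at 90 bpm: 501 × (0.667)^(1/3) = 501 × 0.8736 = 438.

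Neither trips QT >500. Conversely, QT 500 corresponds to a QTcF of about 470 at 50 bpm, 500 at 60 bpm, 550 at 80 bpm and 593 at 100 bpm. The row stands in for QTcF 500 only at 60 bpm. At 80 bpm, values of QTcF from just above 500 to about 550 do not reach it.

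The row can also count someone who meets no protocol limit. A male with QT 510, QTcF 480 and a rise of 35 is in it, yet QTcF is not above 500, QT is not above 600 and the rise is below 60.

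**3. Boundaries.** Take a male at QTcF 450 after a rise of 60 (from 390). Protocol: 60 ≥ 60 and 450 ≥ 450, so the joint limit is met. SAP: 450 > 450 is false and 60 > 60 is false, so he is counted only in >30 to ≤60. The same happens to a female at QTcF 470 after a rise of 60. The protocol also uses ≥450/≥470 at entry (exclusion criterion 9c), so the strict form is the SAP's alone.

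**4. The missing joint row.** Two hypothetical pairs of males, all with QT below 500:

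| Pair | Subject 1: QTcF (rise) | Subject 2: QTcF (rise) | n >450 | n ≤30 | n >60 | n meeting joint limit |
|---|---|---|---|---|---|---|
| A | 455 (+65) | 440 (+20) | 1 | 1 | 1 | 1 |
| B | 455 (+20) | 440 (+65) | 1 | 1 | 1 | 0 |

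The two pairs give identical SAP tables. Every implied Day 1 value (A: 390, 420; B: 435, 375) is below 450, so none breaches the entry threshold.

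**5. The reference.** Write d for the change in QTcF from Day 1 predose to EOT predose, and p for the further change to EOT postdose. Change from Day 1 predose is d + p. Change from EOT predose is p. If d is positive, the second reference understates the on-treatment change by exactly d. The documents do not give d, so no size can be attached to this.

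**The case against.** The SAP does not say that this table exists to audit the stopping rule, and no by-visit count table can identify individuals. Other outputs can: listing 16.2.8.5 gives each subject's ECG data, 16.2.5.1 the dose changes and 16.2.1.1 disposition. Protocol section 6.4.1 requires the reason for stopping study drug to be recorded. With up to 15 subjects, any case can be found by hand. All of this stands, and it limits the point to how the data are summarized.

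A reader might infer that a QTcF above 500 would go unseen. The documents do not support that. Such a value falls in the >450/>470 row, and SAP section 5 includes the maximum in its descriptive statistics, so a by-visit QTcF maximum above 500 would be visible. What is missing is a separate count.

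A reader might also infer that the SAP will understate QTcF change at the end of treatment. That goes too far. SAP baseline is already fixed as the last value before study drug, and the protocol itself writes Day 1 predose and baseline as one thing, so the SAP phrase may name one tracing twice. An EOT predose ECG appears only in the SAP's schedule, which follows amendment 3. In the supplied protocol, predose timing is given for Day 1 only (Table 3, note 8), and subjects take their dose before coming to the final visit (section 7.2.8). The descriptive summary of QTcF change uses baseline without the alternative. Only the outlier categories carry the ambiguity.

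The difference between > and ≥ matters only for values exactly on a boundary. QT >500 may be a slip for QTcF >500, though nothing in the documents says so; if it is, the missing joint row, the missing QT >600 row and the boundaries remain.

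**Conclusion.** The mismatch is real and is one of reporting. No row of the outlier table reproduces a limit in protocol section 4.4, so the table alone cannot count subjects who reached those limits. The absent QTcF >500 and joint rows matter most. The boundary differences are narrow. The reference wording is an ambiguity that could lower the change categories under one reading, by an amount the documents do not allow one to state. Nothing is lost from the data, and stopping decisions do not depend on this table.

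The comparison assumes that the ECG limits in the supplied protocol also applied to the subjects enrolled. SAP section 1.1 says that nobody enrolled under amendments 4 and 5 and that the schedule and listings follow amendment 3, whose stopping text is not supplied.

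**What to change.** First confirm the ECG limits in amendment 3. If they match the supplied text, revise SAP section 5.3.2.1 and table 14.3.5.1.2 as follows:

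- replace or supplement the QT >500 row with QTcF >500 and uncorrected QT >600;
- add a joint row: QTcF rise ≥60 with QTcF ≥450 (males)/≥470 (females);
- set the separate rows to QTcF ≥450/≥470 and to rises of <30, 30 to <60 and ≥60, so that the boundaries match;
- delete the words *or pre-dose* and name Day 1 predose, the SAP baseline, as the only reference.

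Joint criteria already fit the SAP's approach: its Table 1 pairs an absolute value with a change for vital signs, such as systolic pressure >180 mmHg with an increase >40 mmHg. The cost is one paragraph and one table shell, with no new data. The stopping rule itself is not touched.

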5.3.2.2. Clinical Laboratory Assessments

Actual values and changes from baseline in clinical laboratory assessments will be summarized by study visit.

Laboratory values outside the normal range for each parameter will be identified using shift tables. Each subject's hematology and blood chemistry values will be flagged as "low" (below the lower limit of normal/LLN), "normal" (within the normal range), or "high" (above the upper limit of normal/ULN) relative to the normal ranges of the central laboratory. Each subject's urinalysis values will be flagged as "normal" or "abnormal."

Shifts from baseline to high/normal/low status for hematology and blood chemistry parameters will be presented by study visit. Shifts from baseline to normal/abnormal status for urinalysis will be presented by study visit.

5.3.2.3. Adverse Events

Adverse events will be mapped to a Medical Dictionary for Regulatory Activities (MedDRA) preferred term and system organ classification, version 21.0. If a subject experiences multiple events that map to a single preferred term, the greatest severity grade and strongest assessment of relationship to study medication, as determined by the investigator, will be assigned to the preferred term for the appropriate summaries. Adverse events that have a missing severity will be classified as having the greatest severity. Adverse events that have a missing relationship will be classified as having the strongest relationship to study medication.

A summary of TEAEs will be presented to show the number and percentage of subjects with at least one AE, SAE, AESI, related AE, or Grade 3 or higher AE.

The occurrence of TEAEs will be summarized by treatment group using system organ class, preferred term, and severity. Separate summaries of treatment-emergent SAEs, AESI, TEAEs related to study drug, and TEAEs leading to the discontinuation of study treatment, and TEAEs by CX-8998 dose administered will be generated. Adverse events will be assigned to a respective CX-8998 according to the start date of the adverse event.

All TEAEs will be listed for individual subjects. The listing will show both verbatim and preferred terms, along with the system organ class and other data gathered regarding the event. All AEs that have start dates prior to the initiation of study treatment will be excluded from the tables but will be included in the listings.

Determination of treatment emergence will be determined according to the rules outlined in Section 3.3.5.

The following are considered AEs of special interest: increase in seizure frequency, new seizure type, and status epilepticus. Otherwise; seizures are not reported as AEs or SAEs.

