## 4.6 Dose Adjustments / Toxicity Management

Adverse events will be graded for intensity by the investigator (see [Section 10.2.2.2](#)).

Dosing will be discontinued for all study drug-related SAEs.

A member of the study staff will contact any subject who is suspected of experiencing neuropsychiatric AEs to determine the need for an unscheduled visit before further dose escalation may proceed. Subjects who are experiencing any AEs may also be asked to return for an unscheduled visit. Subjects who are suspected of experiencing a neuropsychiatric event should be seen in person.

In all subjects with intolerable AEs (as defined in [Section 10.2.1](#)) that are considered related to study drug, treatment should be suspended for up to 48 hours or until the AE resolves to a tolerable level of severity, whichever is earlier. In subjects who are unable to tolerate 6 mg BID, 8 mg BID or 10 mg BID, dosing may then be resumed at a previously tolerated lower dose. Only a single dose-step reduction (i.e., 10 mg BID to 8 mg BID, 8 mg BID to 6 mg BID, or 6 mg BID to 4 mg BID) is permitted. Reescalation of the dose is NOT permitted. Dosing should be discontinued if there is recurrence of intolerable AEs after the dose reduction. Subjects who experience intolerable AEs while receiving the 2 mg BID or 4 mg BID dose will be discontinued from treatment. Table 2 details dose reductions by dose level.

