5.3.2.6. Epworth Sleepiness Scale.....	22
5.3.2.7. UM-PDHQ.....	22
5.4. Pharmacokinetic Analyses	23
6. PROTOCOL DEVIATIONS.....	23
7. CHANGES IN THE PLANNED ANALYSES FROM THE PROTOCOL	23
8. REFERENCES.....	24
9. PROGRAMMING CONVENTIONS	25
10. PROPOSED TABLES, LISTINGS, AND FIGURES.....	27

1. **INTRODUCTION**

This document describes the statistical methods and data presentations to be used in the summary and analysis of data from Protocol CX-8998-CLN2-002. Background information is provided for the overall study design and objectives. The reader is referred to the study protocol and electronic case report forms (eCRFs) for details of study conduct and data collection.

1.1. **STUDY OVERVIEW**

CX-8998-CLN2-002 is a Phase 2a, open-label study consisting of a screening period of up to 4 weeks and a 4- dose-titration treatment period to dose of up to 10 mg twice daily (BID) of CX-8998, followed by a 1-week safety follow-up period after the last dose of study medication.

Eligible subjects will receive titrating doses of CX-8998 up to 10 mg BID as follows:

1. Days 1 – 2: 2 mg (1 capsule) BID (4 mg/d);
2. Days 3 – 8: 4 mg (2 capsules) BID (8 mg/d);
3. Days 9 – 14: 6 mg (3 capsules) BID (12 mg/d);
4. Days 15 – 20: 8 mg (4 capsules) BID (16 mg/d);
5. Days 21 – 26: 10 mg (5 capsules) BID (20 mg/d);
6. Day 27: 10 mg (5 capsules) (10 mg/d) (once, morning dose only).

Study drug should be administered with food. Subjects should be instructed to take their daily dose at approximately the same times each day. Consecutive doses should be taken no closer than 10 hours and no later than 14 hours (every 12 hours \pm 2 hours). Subjects will remain under observation for at least four hours post-dosing prior to discharge at Visit 1.

At clinic visits at which PK blood draws are scheduled in the afternoon, subjects will take the morning dose at the appropriate time. Both the time of the morning dose and the time of the PK blood draw will be recorded.

A missed dose (>14 hours since the prior dose) should be skipped and should not be “doubled-up” or “made up”; the next dose should be taken 24 hours from the last administered dose. If the subject experiences emesis following the dose, that dose should not be re-taken; instead the next dose should be taken 24 hours from the last administered dose without emesis. If emesis occurs, the subject should contact the investigator or qualified designee at the study site for guidance on management of the emesis.

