5.1. SUBJECT DISPOSITION, DEMOGRAPHIC AND BASELINE CHARACTERISTICS, AND EXTENT OF EXPOSURE

Subject disposition will be presented for all enrolled subjects. The number of subjects enrolled will be presented for each study population and site. The number of subjects who completed the study and discontinued from the study will be provided. The primary reasons for discontinuation from the study at any point also will be presented. Days on study will be summarized.

Demographic data and baseline characteristics including age, gender, race, ethnicity, height, weight will be summarized using descriptive statistics for the ITT population.

Extent of exposure will be summarized for the safety population using the following measures: days on study drug and total study drug received (in mg), as estimated by the number of capsules dispensed and returned. Treatment compliance also will be summarized. The number and percentage of subjects requiring a dose reduction will be summarized.

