9. PROGRAMMING CONVENTIONS

- Page orientation, margins, and fonts: Summary tables, listings, and figures will appear in landscape orientation. There should be a minimum of a 1.25" boundary on the upper (bound) edge, and a minimum of a 1.0" boundary on the remaining three edges. Output should be printed in Courier New with a point size of 8. Titles may be printed using a larger font (e.g., point size 10).
- Identification of analysis population: Every summary table and figure should clearly specify the analysis population being summarized. Listings will be prepared for the ITT Population.
- Group headers: In the summary tables, the group headers will identify the summary group and the sample size for the indicated analysis population. Of note, the header's sample size does not necessarily equal the number of subjects actually summarized within any given summary module; some subjects in the analysis population may have missing values and thus may not be summarized.
- Suppression of percentages corresponding to null categories: When count data are presented as category frequencies and corresponding percentages, the percent should be suppressed when the count is zero in order to draw attention to the non-zero counts.
- Presentation of sample sizes: Summary modules should indicate, in one way or another, the number of subjects actually contributing to the summary statistics presented in any given summary module. As mentioned above, this may be less than the number of subjects in the analysis population due to missing data.
 - In the quantitative modules describing continuous variables (and thus presenting sample size, means, and standard deviations), the sample size should be the number of non-missing observations. The number of missing observations, if any, will be noted.
 - For categorical variables that are presented in frequency tables, the module should present the total count in addition to the count in each category. Percentages should be calculated using this total as the denominator, and the percentage corresponding to the sum itself (that is, 100%) should be presented so as to indicate clearly to a reviewer the method of calculation. The number of missing observations, if any, will be noted.
- Sorting: Listings will be sorted by subject number, date, and parameter, if applicable. If a listing is sorted in a different manner, a footnote will indicate as such.

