14.3.1.1 Summary of Treatment-Emergent Adverse Events

14.3.1.2 Treatment-Emergent Adverse Events by System Organ Class, Preferred Term, and Greatest Severity

14.3.1.3 Treatment-Emergent Adverse Events Related to Study Drug by System Organ Class and Preferred Term

14.3.1.4 Treatment-Emergent Adverse Events by CX-8998 Dose Administered, System Organ Class, and Preferred Term

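### SAP Table 14.3.1.4 (TEAEs by dose) specifies neither the subjects nor the subject-days at each dose, and two SAP rules differ on when treatment emergence ends

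*SAP*

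**What the plan says.** **The table.** SAP section 10 lists "14.3.1.4 Treatment-Emergent Adverse Events by CX-8998 Dose Administered, System Organ Class, and Preferred Term", by title only. Section 5.3.2.3 gives the allocation rule: "Adverse events will be assigned to a respective CX-8998 according to the start date of the adverse event". A noun is missing after the drug name; from the table title it is presumably the dose.

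**The dosing steps.** SAP section 1.1 sets 2 mg BID on Days 1–2, 4 mg BID on Days 3–8, 6 mg BID on Days 9–14, 8 mg BID on Days 15–20 and 10 mg BID on Days 21–26. It then adds "Day 27: 10 mg (5 capsules) (10 mg/d) (once, morning dose only".

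**Exposure and denominators.** SAP section 5.1 summarises "days on study drug and total study drug received (in mg"). It adds: "The number and percentage of subjects requiring a dose reduction will be summarized". Neither is broken down by dose level. SAP section 9 says that "the group headers will identify the summary group and the sample size for the indicated analysis population"; for this table that population is the Safety Population. Section 9 also asks each module to show how many subjects contribute, and it uses the module total as the denominator for categorical percentages.

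**Treatment emergence.** SAP section 3.3.7 confines TEAEs to the treatment period, which it ends at Day 27. Section 5.3.2.3 points elsewhere: "Determination of treatment emergence will be determined according to the rules outlined in Section 3.3.5". Section 3.3.5 offers additional criteria for AEs with missing start or stop dates. The first counts any event that starts later than the first-dose date and sets no upper limit. AEs are collected through the EOS contact on Day 33 (SAP section 1.2, footnote 19).

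**The concern.** Safety and tolerability is the primary objective, TEAEs head the list of safety endpoints, and Table 14.3.1.4 is the only listed table that sets AEs against dose. Its columns cover very different lengths of time and possibly different numbers of subjects. If it shows only crude counts and percentages, a reader cannot tell from the table how far a rise across columns reflects dose, days at that dose, or who was still being treated.

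The second issue affects the TEAE tables generally. With two rules for when treatment emergence stops, two programmers could follow the SAP and still disagree on whether the same late AE is a TEAE. If it is counted, the by-dose table has no dose to assign to its start date.

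**Working it through.** There is no plan figure to reproduce: SAP section 3.1 says that the sample size has no statistical basis. As a check on the calendar, 2 + 6 + 6 + 6 + 7 = 27 days, which agrees with the Day 27 end of treatment in section 3.3.7.

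**1. Time at risk by design** (section 1.1; N = 15 from section 3.1; all subjects on schedule, so these are upper limits)

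| Step | Days | Subject-days (days × 15) |
|---|---|---|
| 2 mg BID | 2 | 30 |
| 4 mg BID | 6 | 90 |
| 6 mg BID | 6 | 90 |
| 8 mg BID | 6 | 90 |
| 10 mg (including Day 27) | 7 | 105 |

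**2. Effect of unequal time on crude incidence.** The documents give no TEAE rate, so I assume a constant daily rate h, equal at every dose. The chance of at least one TEAE in d days is 1 − exp(−dh). The ratio of a 6-day to a 2-day step is [1 − exp(−6h)] / [1 − exp(−2h)]:

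- h = 0.01: 2.94
- h = 0.03: 2.83
- h = 0.05: 2.72 (25.9% against 9.5%, or 3.9 against 1.4 of 15 subjects)
- h = 0.10: 2.49

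**3. Clustering after a dose increase.** Keep rate h on days 1–2 of a step and use h/k on days 3–6. The 6-day cumulative rate is then 2h + 4h/k.

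- k = 2: ratios 1.98, 1.94, 1.90, 1.82
- k = 5: ratios 1.39, 1.38, 1.37, 1.35
- no events after day 2: ratio 1.0

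**4. Denominator.** Suppose 4 subjects have a TEAE at 10 mg BID (illustration). On the subjects who received that dose, this is 4/13 = 31% or 4/10 = 40%; on a fixed 15 it is 4/15 = 27%. Attrition on a fixed N works against the ratio in step 2. It would cancel it only if about 1/2.94 = 34% to 1/2.49 = 40% of subjects remained.

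**5. The two emergence rules side by side.** Take an AE that starts on Day 30 and is still ongoing, so has no stop date.

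- Section 3.3.7: Day 30 is after Day 27, so it is not a TEAE.
- Section 5.3.2.3 with section 3.3.5: it starts after the first dose, so it is a TEAE.
- By-dose allocation: no dose is taken on Day 30, so the start-date rule gives no column.

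The disputed window is 33 − 27 = 6 days, or at most 6 × 15 = 90 subject-days.

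**6. AEs without a start date.** Section 3.3.5 counts these as treatment-emergent if the stop date is after the first dose or is also missing. Allocation by start date then gives no column. If the fallback imputation in section 3.3.5 is applied instead, the missing parts are taken from Day 1, and a wholly undated AE falls in the 2 mg BID column, the one with the least exposure.

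**The case against.** The strongest reply has several parts.

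- **Section 9 does more than set a header N.** It says the header need not match the number summarised, asks for the contributing count and uses the module total as denominator. This stands. A reader might infer that percentages at the higher doses will be diluted by a fixed N of 15. The documents show only that this is possible: table shells are not among them, and the contributing count is never defined as the subjects who received a given dose.
- **Section 3.3.5 is about incomplete dates.** It can be read as a supplement to section 3.3.7, which narrows the conflict. It does not remove it, because an ongoing AE has no stop date and so falls within the narrow reading.
- **Everything can be rebuilt from listings.** Dose changes, AICure dosing and AEs are listed by subject, and there are at most 15 subjects. That is true, but it leaves the reader to construct the denominators of a primary safety table.
- **Rates are a matter of taste in a descriptive study.** This stands. With 2 events in 30 subject-days the rate is 6.7 per 100 (exact Poisson 95% interval 0.8 to 24.1); with 4 in 105 it is 3.8 (1.0 to 9.8). Repeat events within a subject would make those intervals too narrow. A rate column is therefore optional.
- **The dose-reduction limits in Protocol section 4.6** come from a protocol without Day 27 dosing. SAP section 1.1 says that no subject enrolled under Amendments 4 and 5 and that Amendment 5 removed that dosing. They are not needed here: SAP section 5.1 itself expects discontinuations and dose reductions.

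**Conclusion.** The point holds and is minor. The SAP plans a by-dose TEAE table over steps of 2 to 7 days without specifying number at risk or time at risk per column. It also gives two rules for the end of treatment emergence, which differ at least for AEs with no stop date that start on Days 28 to 33.

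The factor of 2.5 to 2.9 rests on an assumed constant daily rate of 0.01 to 0.10, equal across doses. With early clustering it lies between 1.0 and 2.0. Neither figure predicts the table: with at most 15 subjects, chance and attrition can move the columns either way. A reader might infer that the plan will manufacture an apparent dose-response; the documents support only that a real one could not be told apart from unequal exposure. A reader might also infer that AEs on Days 28 to 33 would inflate the 10 mg column, but the SAP never places them there. Nor is the Day 26 end of treatment in the protocol against Day 27 in the SAP part of this point, since SAP section 1.1 explains it.

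**What to change.** 1. In Table 14.3.1.4, set each dose column's N to the subjects who received at least one dose at that level, and use it as the percentage denominator. Supply the missing noun in the allocation sentence of section 5.3.2.3.
2. Show subject-days at each level, from the dose change log (listing 16.2.5.1) and the AICure data (16.2.5.2), with a footnote that forced titration confounds dose with time on study. TEAEs per 100 subject-days may be added, labelled descriptive.
3. State one end date for treatment emergence and use it in sections 3.3.5, 3.3.7 and 5.3.2.3.
4. Put AEs that start after the last dose, or that have no start date, in a separate category of the by-dose table.

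The cost is small: two header rows, one extra category, a footnote and an aligned definition, all from data already planned for listing. The output grows slightly and stays imprecise, and the added rows make exposure visible without isolating a dose effect.
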